**¹¹C-METHIONINE, 2-[¹⁸F]-FLUORO-2-DEOXY-D-GLUCOSE, AND [¹⁸F]-
DIHYDROTESTOSTERONE (FDHT) PET IMAGING IN PATIENTS WITH PROGRESSIVE
PROSTATE CANCER**

1.0	PROTOCOL SUMMARY:	3
2.0	OBJECTIVES:	3
3.0	RATIONALE AND BACKGROUND	4
3.1	DISEASE INFORMATION	4
3.2	CONVENTIONAL IMAGING MODALITIES	5
3.3	POSITRON EMISSION TOMOGRAPHY	5
3.4	EQUIPMENT INFORMATION (PET)	7
3.5	STANDARD EVALUATION SCHEMA	7
4.0	BACKGROUND DRUG INFORMATION	8
5.0	PATIENT ELIGIBILITY	8
6.0	PRETREATMENT EVALUATION	9
7.0	TREATMENT PLAN	9
8.0	TOXICITY ASSESSMENT AND MANAGEMENT	11
9.0	GUIDELINES FOR REPORTING ADVERSE DRUG REACTIONS	11
10.0	CRITERIA FOR REMOVAL FROM STUDY	11
11.0	DATA ANALYSIS	12
12.0	BIOSTATISTICAL CONSIDERATIONS	12
13.0	SUBJECT REGISTRATION	13
14.0	PROTECTION OF HUMAN SUBJECTS	13
15.0	INFORMED CONSENT PROCEDURES	14
16.0	BIBLIOGRAPHY	Z15

STUDY COORDINATORS:

[name]. [contact]
[name]. (*) [contact]
Mentor: [name](*) [contact]

DEPARTMENT OF DIAGNOSTIC RADIOLOGY:

Nuclear Medicine/Cyclotron : [name], [name], [name], [name]

Medical Imaging: [name].

DEPARTMENT OF MEDICAL PHYSICS:

[name], [name]

GENITOURINARY ONCOLOGY SERVICE, DEPARTMENT OF MEDICINE:

[name],* [name], PhD*; [name]; [name]; [name]; [name]; [name]; [name], PhD.

DIVISION OF HEMATOLOGIC ONCOLOGY:

[name].

DEPARTMENT OF BIOSTATISTICS AND EPIDEMIOLOGY:

[name].

DEPARTMENT OF CLINICAL CHEMISTRY:

[name].

CLINICAL TRIALS OFFICE:

[name]

(*) designated to obtain informed consent

MEMORIAL SLOAN-KETTERING CANCER CENTER
[name]
[name]
[contact]

1.0 PROTOCOL SUMMARY:

The imaging modalities used to monitor prostate cancer in man are limited. The disease typically spreads to osseous sites, where changes are difficult to quantitate on a serial basis. The proposed trial is the first in a series of studies designed to evaluate the biology of prostate cancer *in vivo* using PET imaging. It is based on the ability of positron emitting radiopharmaceuticals to serve as tracers of biologic events. In this study, we will examine the metabolic properties of ¹¹C-methionine and FDG in prostate cancer by PET imaging.

Initially, we will define the degree of correlation between FDG or C-11-methionine and standard imaging modalities such as CT/MRI and bone scans. We have observed discordance between uptake of [¹¹C]-methionine (CMET) and FDG in individual sites.(1) Pilot studies have given us a basis for estimates of variability and differences between FDG and CMET, and kinetic data has led to the design of acquisition protocols that make whole body PET imaging of CMET practical in patients. As such, we will continue to compare on a site by site basis the uptake of ¹¹C-methionine and FDG by performing whole body PET imaging following each radiopharmaceutical administration. Comparisons will be made to bone scintigraphy using 99m-Tc scanning, computed tomography, and, when clinically indicated, magnetic resonance imaging to assess whether sites detected by PET imaging are identified using standard imaging techniques and *vice versa*. Also, where tumor sites are identified on PET scans, a semiquantitative index, the standardized uptake value (SUV), as well as related parameters of total lesion metabolism (TLM) will be calculated as an objective measurement. In selected patients, imaging will be performed with F-18 fluoro dihydrotestosterone (FDHT), obtained through a collaboration with [name]. of Washington University, St. Louis.(2)

We will also define the utility of PET as an outcome measure following treatment by assessing the effects of treatment on SUV. Selected patients will be asked to undergo follow-up PET scanning along with follow-up bone scintigraphy, CT or MRI, where clinically appropriate.

All patients with histologically documented progressive prostate cancer are eligible, including those with localized disease, rising PSA, non-castrate metastatic, and castrate metastatic disease. Progression may be defined either by a rise in PSA of $\geq 50\%$, development of new bone lesions or an increase in pre-existing lesions, or an increase in measurable disease.

Patients will undergo PET scanning using either FDG either alone or with CMET or DHT (performed the day following the FDG scan). Serum will be drawn to define the pharmacokinetic properties of the tracer. Serial PET scans will be performed at baseline, four weeks, and twelve weeks and six months, in conjunction with bone scanning, CT/MRI, where clinically appropriate, unless the patient is on a clinical trial that dictates otherwise. These will be compared with baseline scans and available prior scans .

2.0 OBJECTIVES:

The primary objectives of this study are:

- 2.1 **Homogeneity of the metabolism of prostate cancer metastases:** To explore the FDG and CMET metabolism in tumors by PET in progressive prostate cancer, on a site by site basis.

2.1 **Diagnostic ability:** To explore the diagnostic ability of FDG and, in selected cases ¹¹C-methionine, by comparing PET scanning to standard of care diagnostic studies, which include the 99m-Tc bone scan, computed tomography, and magnetic resonance imaging.

2.2. **Treatment effects:** To explore changes in the relative tumor uptake, as defined by such quantitative measures as the standardized uptake value (SUV) and the total lesion metabolism (TLM), for FDG and ¹¹C-methionine after systemic therapy(ies). To determine which tracer, FDG or CMET, surrogates for glucose metabolism and amino acid synthesis respectively, is the superior predictor of treatment response.

2.3 FDHT Imaging: In selected patients who are progressing and have advanced androgen-independent prostate cancer, we will develop pilot data on the in vivo targeting and biokinetics of F-18 FDHT by PET imaging. When feasible, biopsy samples will be obtained from index lesions in order to correlate the level of FDHT uptake with androgen receptor expression, as determined by immunohistochemistry.

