One hypothesis under study in this trial is whether ¹¹C- methionine is more effective in visualizing androgen independent prostate cancer by PET imaging. The essential amino acid, ¹¹C- methionine is a tracer that has been used to image a variety of human tumors.(16-18) In a preliminary report from Nilsson and coworkers, 12 patients with androgen independent prostate cancer underwent PET imaging with ¹¹C- methionine. Uptake of the radiotracer was discovered in all known sites of bone and soft tissue lesions of patients visualized by standard bone scintigraphy or cross sectional imaging.(19) Ten patients had repeat PET scans. Those who responded to treatment had a reduced uptake of the radiotracer with no changes in the images generated by standard techniques. Our ongoing results show that 93% of index lesions were visible using ¹¹C-methionine and 83% visible using FDG.(1) These biodistribution and metabolic findings require additional verification in a larger series.

¹¹C-methionine and ¹⁸FDG whole body imaging

We have performed a preliminary comparative study of ¹¹C-methionine and ¹⁸F-FDG in 10 patients with prostate cancer, who were referred for PET imaging with progressive prostate cancer, as defined by serially rising PSA values and one or more new ("index") lesions on bone scan. Among the 10 patients, there were 13 such index lesions on bone scans. ¹¹C-methionine imaged 12/13 (93%), and ¹⁸F-FDG 11/13 (83%) index lesions. The one lesion not imaged by CMET was subsequently judged to be avascular necrosis, based on its pattern of resolution on subsequent bone scans. ¹¹C-methionine is very rapidly cleared from the blood, with rapid equilibration (10 minutes) in the tumor. The tumor uptake of ¹¹C-methionine is consistently high, with standard uptake values (SUVs) ranging from 4.9 to 11.6. We have therefore shown that high-quality whole body PET imaging is feasible with ¹¹C-methionine, despite the short 20-min physical half-life of carbon-11.

As accrual to the study has been limited by the need to generate ¹¹C-methionine immediately prior to administration, and based on our preliminary results showing that a higher percentage of tumors are visualized with FDG than previously anticipated, we plan to perform FDG scans in all patients, and ¹¹C-methionine when it is available. In cases where uptake is visible with FDG, repeat studies will be conducted after therapeutic intervention.

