12.0 BIOSTATISTICAL CONSIDERATIONS

To assess the diagnostic implications of PET scanning with ¹¹C-methionine and FDG, the sensitivity and specificity will be estimated by comparing PET scan results to "standard of care" diagnostic measures that include the 99m-Tc bone scan, computed tomography, and magnetic resonance imaging. Each patient will receive these standard diagnostic measures and PET scanning with both ¹¹C-methionine and FDG. The diagnostic

"standard of care" scan (bone scan, CT or MRI) will be recorded as positive or negative for each site: bone and bone marrow and/or soft tissue

The sensitivity of PET imaging with ^{11}C -methionine or FDG is defined as the ability of PET scanning to identify those metastatic lesions diagnosed by standard diagnosis using bone scan, CT, or MRI as "gold standard" and is determined by the proportion of patients with positive lesions as diagnosed by standard method who were identified by the PET imaging. The sensitivity will be measured for both androgen-dependent and androgen-independent prostate cancer patients, and on a site by site basis (bone and bone marrow, and soft tissue).

Assuming at least one site in each patient is assessed positive by the gold standard, the sensitivity of FDG and ^{11}C -methionine can be conservatively estimated to within ± 0.16 . The total sample size for this study is 265.

To explore changes in metabolism during treatment based on PET imaging, the average SUV value will be recorded at 4 weeks, 12 weeks, and 6 months following the baseline scan. Summary measures such as the slope of the SUV trajectory and the area under the SUV curve will be recorded separately for FDG and ^{11}C -methionine.

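### The plan conflicts on who receives methionine PET, and nothing keeps that choice, or the choice of repeat scans, independent of the FDG result

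*Combined protocol and SAP*

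**What the plan says.** Four places address who receives methionine.

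- Section 2.0, objective 2.1 (Diagnostic ability): "To explore the diagnostic ability of FDG and, in selected cases", methionine. No criterion is given.
- Section 3.3: "we plan to perform FDG scans in all patients, and ¹¹C-methionine when it is available". The reason given is that "accrual to the study has been limited by the need to generate ¹¹C-methionine immediately prior to administration".
- Section 1.0: patients are scanned "using either FDG either alone or with CMET or DHT (performed the day following the FDG scan").
- Section 12.0: every patient is said to have the standard imaging and PET with both tracers.

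Two places address who is scanned again. Section 3.3 says: "In cases where uptake is visible with FDG, repeat studies will be conducted after therapeutic intervention". Section 1.0 says: "Selected patients will be asked to undergo follow-up PET scanning", again with no criterion. Section 7.8 permits serial scans at 4 weeks, 12 weeks and 6 months and does not repeat the FDG condition.

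Objective 2.2 asks which of the two tracers better predicts treatment response. For that objective Section 12.0 provides that "the slope of the SUV trajectory and the area under the SUV curve will be recorded separately" for each tracer. It names no paired analysis set and does not say what happens when a visit has FDG but no methionine.

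**The concern.** A comparison of two tests in the same patients is protected from selection only if having both tests does not depend on the result of either. If methionine is ordered with the FDG result in hand, restricting the analysis to patients with both scans does not help, because membership of that set already depends on FDG. The same holds over time: if repeat scans follow visible FDG uptake, a patient whose disease shows on methionine but not on FDG need not enter the series that objective 2.2 relies on. Section 1.0 reports discordance between the tracers at individual sites, so such patients are plausible.

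A second mechanism needs no dependence on FDG. Methionine must be made immediately before use, so it may be missing at some visits. A slope or area computed from fewer visits can differ from the FDG summary even when the two tracers behave identically. At stake are the head-to-head question in objective 2.2 and the hypothesis in Section 3.3 that methionine visualizes androgen-independent disease better.

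**Working it through.** **1. The four statements.** Objective 2.1, Section 3.3 and Section 1.0 can be read together if the selected cases are simply those in which methionine was available. Section 12.0 fits none of them. No section fixes the methionine decision before the FDG scan is read or requires a reason to be logged when methionine is omitted. Section 11.0 has each modality evaluated independently, which protects how scans are read but not who is scanned.

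**2. Unequal visits.** Assume one course for both tracers, relative to baseline: 1, 0.6, 0.6, 0.6 at weeks 0, 4, 12 and 26 (6 months taken as 26 weeks).

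- All four visits: mean week 10.5, mean value 0.7. The cross-product sum is -3.15 + 0.65 - 0.15 - 1.55 = -4.20. The sum of squares is 110.25 + 42.25 + 2.25 + 240.25 = 395. Slope = -4.20/395 = -0.0106, or -1.06% of baseline per week.
- Weeks 0 and 26 only: -0.4/26 = -0.0154, or -1.54% per week.
- Trapezoid area per week: (0.8 × 4 + 0.6 × 22)/26 = 16.4/26 = 0.63 from four visits, against 0.80 from weeks 0 and 26.

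The tumor course is the same, but the summaries differ. The course and the missing-visit pattern are assumptions.

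**3. Selection at baseline, as illustration.** The pilot in Section 3.3 found 12/13 index lesions on methionine and 11/13 on FDG, which are 92% and 85% (printed as 93% and 83%). Take 0.92 and 0.85 as true rates, a lead of 7 points. Let f+ and f- be the fractions of FDG-positive and FDG-negative patients who get methionine, with one lesion per patient. Let a and b be the methionine detection rates given FDG positive and FDG negative.

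- FDG rate in the both-scan set = 0.85f+ / (0.85f+ + 0.15f-)
- Methionine rate = (0.85f+·a + 0.15f-·b) / (0.85f+ + 0.15f-)

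Independent tracers have a = b = 0.92. A positively dependent case is a = 0.95, b = 0.75 (check: 0.85 × 0.95 + 0.15 × 0.75 = 0.92).

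| f+, f- | FDG | Methionine, independent / dependent | Lead in points |
|---|---|---|---|
| equal | 0.85 | 0.92 / 0.92 | 7 |
| 0.5, 1 | 0.425/0.575 = 0.739 | 0.920 / 0.898 | 18 / 16 |
| 1, 0.5 | 0.85/0.925 = 0.919 | 0.920 / 0.934 | 0 / 2 |

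When methionine use does not depend on FDG, the true lead is recovered.

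**4. More than one lesion per patient.** The pilot rates are per lesion, and Section 3.4 reports 157 lesions in 18 patients (157/18 = 8.7 each). Suppose two independent lesions per patient, selection on any FDG-visible lesion, and independent tracers. Then 0.15² = 0.0225 of patients are FDG-negative.

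- (0.5, 1): FDG reads 0.425/(0.5 × 0.9775 + 0.0225) = 0.425/0.51125 = 0.831, a lead of about 9 points.
- (1, 0.5): 0.85/(0.9775 + 0.5 × 0.0225) = 0.85/0.98875 = 0.860, a lead of about 6 points.

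The bias is then much smaller than in step 3. Correlated lesions would enlarge it again.

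**The case against.** The strongest reply is that the only stated driver of methionine use is production on the day, which may be unrelated to the FDG result. Section 12.0 even implies no selection at all. Where the plan wants selection on a PET result it says so, as in Section 3.3, where FDHT subjects are chosen for tumors that are active on FDG or methionine. No such wording governs baseline methionine. This stands: a reader might infer that investigators choose methionine patients from the FDG scan, but the documents do not say who selects or on what basis.

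The scan order is also unsettled. The bracket in Section 1.0 may apply to DHT only. Section 7.9 sets a day-after rule for serial FDHT scans, while Section 7.4 sets no order for methionine. So it is not established that the FDG result is known when methionine is ordered. But under either reading no rule keeps the two apart.

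A reader might also infer that an observed advantage of one tracer would be purely an artefact of selection. The scenarios above start from a true 7-point lead and do not show that. It would require selection fractions and a degree of agreement between tracers that the documents do not give.

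Finally, most objectives are exploratory, and objective 2.1 compares PET with standard imaging, not tracer with tracer. That limits the weight of the point for 2.1. Objective 2.2, however, is explicitly comparative. The repeat rule stands in a background section and does not expressly bar repeat scans in other patients, but nothing in Section 7.8 or 12.0 overrides it.

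**Conclusion.** The point holds in three parts. First, the documents contradict each other on who receives methionine, and Section 12.0 is at odds with the other three statements. Second, repeat studies are tied in writing to visible FDG uptake, so the follow-up that serves objective 2.2 is selected on one of the two tracers under comparison. Third, per-tracer slope and area without matched visits can differ for an identical course (-1.06% against -1.54% per week in the example) if methionine is missing at some visits.

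Selection bias at baseline is possible, not demonstrated. Its size and direction cannot be derived from the documents. The leads of 16 to 18 and 0 to 2 points rest on one lesion per patient and assumed selection fractions. With two independent lesions and independent tracers, the same fractions give about 9 and 6 points against a true 7.

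**What to change.** 1. Reconcile Section 1.0, objective 2.1, Section 3.3 and Section 12.0 on who receives methionine. If it is not universal, correct the Section 12.0 sentence that says every patient has both tracers.
2. In objective 2.1, replace the selected-cases wording with a rule: methionine is assigned at scheduling from production availability, before that patient's FDG scan is read, and the reason is logged when it is not done.
3. In Section 12.0, state that FDG and methionine are compared only on patient-visits with both scans, with slope and area for both tracers computed from the same visits. FDG-only visits stay in the FDG description.
4. Either state that the objective 2.2 comparison applies only to FDG-visible patients for as long as repeat studies depend on visible FDG uptake, or reword the Section 3.3 rule so that it does not depend on one tracer. Step 3 alone does not remove this selection.

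The cost is amendment wording, one scheduling rule and a log entry. FDG visits without methionine drop out of the tracer comparison and nothing else.

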3.0 RATIONALE AND BACKGROUND

[figure not shown]
3.1 Disease Information

The patterns of spread of prostate cancers make it difficult to quantify tumor regression and progression in a reproducible way, because the standard phase II response criteria do not apply.(3) Bone, the most common site of spread, is particularly difficult because tumor growth in the marrow results in osteoblastic changes on plain radiographs which, in the end stage, results in complete replacement of the marrow space. While most physicians accept that sclerotic healing of a lytic lesion constitutes tumor regression, the sequential monitoring of lesions that are initially sclerotic is problematic as histologic reversion to a normal bone architecture rarely occurs. Even if all tumor cells are destroyed there may be no visible plain radiographic changes. In these cases, only a direct biopsy can determine if viable tumor cells are present.

To circumvent this problem, and before the availability of PSA measurements, many investigators restricted entry on clinical trials to selected patients with bi-dimensionally measurable tumor masses.(4) This excluded the majority of patients from trials. Others attempted to assess response by combining subjective parameters, such as changes in performance status or pain relief, with indirect objective measures such as changes in hemoglobin or weight.(5) Over the past five years, we have developed a clinical trial methodology to evaluate new therapeutic approaches based on serial PSA determinations.(6) Entry requires clear documentation of disease progression, controlling for the hormone sensitivity of the tumor,(7) controlling for steroid hormone withdrawal responses,(8) and reporting the outcomes of the trial on the basis of post-therapy changes in PSA, measurable disease, and radionuclide imaging independently.(6) The definition of progression includes serial elevations in PSA values, which have been shown to antedate clinical and radiographic evidence of progression for patients with both hormone-naïve and hormonally relapsing disease.

More recently, we developed a clinical states model for progression that highlights easily recognized clinical milestones, and provides a background to determine when to recommend treatment, to select a particular approach, and to assess treatment effects.(9) In this trial, patients with progressive disease in all disease states will be studied.

3.2 Conventional Imaging Modalities

Radionuclide bone scanning: Standard bone scintigraphy is limited because it reflects the reaction of bone to surrounding cancer rather than providing a direct measure of cancer activity. In one series of patients with a total of 100 bone scan abnormalities, 57 were confirmed by plain radiographs, and 42 showed normal corresponding plain radiographs; and 1 patient had a radiographic abnormality not detected by scintigraphy.(10) The flare phenomenon, a paradoxical increase in intensity after successful therapy, further complicates the interpretation of scans on a serial basis.(11) To begin to address these questions, we have developed a novel bone scan index,(12) which quantifies the percentage of bone involved by tumor, but this too does not provide an index of the viability of tumor.

Cross sectional imaging: Cross-sectional imaging modalities used in the evaluation of prostate cancer include computed tomography (CT) and magnetic resonance imaging (MRI). The utility of each of these modalities varies according to stage of the disease. CT is well suited for the detection of soft tissue disease, but has limited utility in assessing early changes in bone. It is not sensitive in detecting microscopic nodal disease or for detecting tumor in non-enlarged lymph nodes. In our experience, CT is also limited in evaluating disease confined to the prostate and adjacent area. MRI imaging is considered the modality of choice for the most accurate assessment in the region of the prostate, neurovascular bundles and seminal vesicles.(13) MRI can also detect soft tissue disease and is most useful to corroborate bone scintigraphic findings, since the earliest involvement is thought to be present in the bone marrow. MRI exhibits the highest sensitivity in the axial skeleton and pelvis, and is less effective in the ribs, chest wall, and skull.

3.3 Positron Emission Tomography

Positron Emission Tomography (PET) has the potential to detect the altered metabolism of the malignant state. This may improve detection as well as permit the quantitative monitoring of metabolic changes in tumors that are under treatment. Of the many radiopharmaceuticals used for PET scanning, the glucose analogs have been highly successful for imaging of a variety of human tumors and for monitoring response to therapy.(14) However, in a trial using FDG and PET imaging in androgen independent prostate cancers at MSKCC, only 18% of the metastatic sites detected by conventional bone scintigraphy metabolized FDG sufficiently to be visualized on PET imaging(14). Our preliminary results for this study show that over 70% of the abnormalities visualized on radionuclide bone scan are visible using FDG. This shows the importance of

controlling for disease progression prior to imaging as is required in this trial.(1) Recently, [name] and coworkers studied the uptake of FDG in the androgen-dependent human prostate cancer xenograft CWR-22. High uptake values were recorded, but of greater interest was the finding that FDG uptake decreased within 24 hours following castration. The decrease preceded declines in PSA, suggesting that PET imaging may be useful to monitor the response to treatment.(15) This suggests that for many patients, serial changes in FDG may be useful to monitor disease status. One limitation of the study, however, was that entry did not require a strict definition of disease progression prior to imaging.

One hypothesis under study in this trial is whether ¹¹C- methionine is more effective in visualizing androgen independent prostate cancer by PET imaging. The essential amino acid, ¹¹C- methionine is a tracer that has been used to image a variety of human tumors.(16-18) In a preliminary report from Nilsson and coworkers, 12 patients with androgen independent prostate cancer underwent PET imaging with ¹¹C- methionine. Uptake of the radiotracer was discovered in all known sites of bone and soft tissue lesions of patients visualized by standard bone scintigraphy or cross sectional imaging.(19) Ten patients had repeat PET scans. Those who responded to treatment had a reduced uptake of the radiotracer with no changes in the images generated by standard techniques. Our ongoing results show that 93% of index lesions were visible using ¹¹C-methionine and 83% visible using FDG.(1) These biodistribution and metabolic findings require additional verification in a larger series.

¹¹C-methionine and ¹⁸FDG whole body imaging

We have performed a preliminary comparative study of ¹¹C-methionine and ¹⁸F-FDG in 10 patients with prostate cancer, who were referred for PET imaging with progressive prostate cancer, as defined by serially rising PSA values and one or more new ("index") lesions on bone scan. Among the 10 patients, there were 13 such index lesions on bone scans. ¹¹C-methionine imaged 12/13 (93%), and ¹⁸F-FDG 11/13 (83%) index lesions. The one lesion not imaged by CMET was subsequently judged to be avascular necrosis, based on its pattern of resolution on subsequent bone scans. ¹¹C-methionine is very rapidly cleared from the blood, with rapid equilibration (10 minutes) in the tumor. The tumor uptake of ¹¹C-methionine is consistently high, with standard uptake values (SUVs) ranging from 4.9 to 11.6. We have therefore shown that high-quality whole body PET imaging is feasible with ¹¹C-methionine, despite the short 20-min physical half-life of carbon-11.

As accrual to the study has been limited by the need to generate ¹¹C-methionine immediately prior to administration, and based on our preliminary results showing that a higher percentage of tumors are visualized with FDG than previously anticipated, we plan to perform FDG scans in all patients, and ¹¹C-methionine when it is available. In cases where uptake is visible with FDG, repeat studies will be conducted after therapeutic intervention.

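### Section 12 plans a separate sensitivity for each tracer and no paired comparison, although Section 3.3 makes methionine's advantage a hypothesis under study

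*Combined protocol and SAP*

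**What the plan says.** - **The question.** Section 3.3 introduces it with "One hypothesis under study in this trial is whether" CMET "is more effective in visualizing androgen independent prostate cancer by PET imaging". The sentence names no comparator. FDG is the natural reading, because the surrounding text reports low FDG visualization in an earlier androgen-independent series and then gives pilot detection rates for both tracers.
- **The intent to compare.** Section 1.0 says "we will continue to compare on a site by site basis the uptake of" the two tracers, with whole body imaging after each. It gives no method.
- **The planned analysis.** Section 12 estimates sensitivity and specificity of each tracer against bone scan, CT or MRI. On subgroups it says "The sensitivity will be measured for both androgen-dependent and androgen-independent prostate cancer patients, and on a site by site basis". SUV slope and area under the curve are also summarized separately by tracer. No difference between tracers, paired method or interval for a difference appears.
- **Who gets CMET.** Section 3.3 says "we plan to perform FDG scans in all patients", with CMET added when it is available. Section 2.0 limits CMET to selected cases for the diagnostic objective, and Section 1.0 allows FDG alone. Section 12 says every patient receives both.
- **Precision.** Section 12 states that each tracer's sensitivity "can be conservatively estimated to within ± 0.16" and that "The total sample size for this study is 265".

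**The concern.** The question is comparative, but the planned output is two one-sample estimates. Anyone answering the question from that output has to set the two sensitivities beside each other. If CMET is given only to some patients, the FDG figure includes patients who never had CMET. Availability of the tracer, or selection of cases, may be related to disease state, lesion burden or calendar time, and any such relation shows up as a tracer difference.

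If all patients have both scans, the difference between the two sensitivities is estimated correctly, but its uncertainty is not. That depends on how many lesions one tracer shows and the other misses, and separate estimates do not report this. Either way, a reader of the final report could not tell how far the data support the hypothesis.

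**Working it through.** **1. The plan's own figure.** The half-width of a single proportion is 1.96 × √(p(1−p)/n). At p = 0.5 and an assumed 95% level, ±0.16 needs n = 0.25 × (1.96/0.16)² = 37.5, so 38. At n = 265 the half-width is 1.96 × √(0.25/265) = 0.060. The stated ±0.16 therefore does not come from 265. That is a separate matter. What counts here is that the figure describes one tracer's sensitivity and not a difference.

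**2. The pilot figures (Sections 3.3 and 3.4).** In the same 13 index lesions, CMET showed 12 (92.3%) and FDG 11 (84.6%), a difference of 1/13 = 7.7 points. The discordant split is 1-0 if CMET's miss was also missed by FDG, and 2-1 otherwise. Exact McNemar gives p = 1.0 in both cases. Set beside the 71% FDG concordance in the separate 157-lesion series, the same CMET figure gives 92.3 − 71 = 21.3 points. The two FDG series differ in lesion definition, so this shows only how the result depends on which FDG patients are used. It does not estimate bias in this trial.

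**3. If CMET goes to a subset.** Let m of 265 patients have both scans, with true sensitivity 0.85 for both tracers. Let FDG-only patients have FDG sensitivity 0.85 − g. FDG sensitivity over all patients is then 0.85 − g(1 − m/265), so the expected spurious CMET advantage is g(1 − m/265).

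| m | g = 0.14 | g = 0.05 | g = 0 |
|---|---|---|---|
| 38 | 12.0 points | 4.3 | 0 |
| 60 | 10.8 | 3.9 | 0 |
| 100 | 8.7 | 3.1 | 0 |
| 130 | 7.1 | 2.5 | 0 |

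The share of simulated trials in which a pooled two-proportion z-test (two-sided 0.05, assumed; one unit per patient) of CMET in m against FDG in 265 favours CMET:

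| CMET and FDG results in dually scanned patients | g = 0.14 | g = 0.05 | g = 0 |
|---|---|---|---|
| independent | 35-45% | 7-10% | about 2% |
| identical | 33-42% | 2-5% | under 1% |

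Ranges are over the four values of m. The 14-point gap is 0.85 − 0.71. It borrows the 71% lesion concordance as if it were a patient-level rate, so it is an assumption. A gap in the other direction would favour FDG. The paired difference has expectation 0 in every column.

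**4. If every patient has both scans.** Take 100 patients with CMET 92/100 and FDG 85/100, as illustrative counts. Treated as independent samples, the standard error is √(0.92×0.08/100 + 0.85×0.15/100) = 0.045, giving 0.07 with 95% CI −0.018 to 0.158. The paired standard error is √((b+c) − (b−c)²/100)/100, where b and c are the discordant counts:

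| b-c split | 95% CI | exact McNemar p |
|---|---|---|
| 7-0 | 0.020 to 0.120 | 0.016 |
| 8-1 | 0.013 to 0.127 | 0.039 |
| 15-8 | −0.023 to 0.163 | 0.21 |

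The two sensitivities are the same in all three rows. They fix the difference but not its interval.

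**5. Clustering.** The Section 3.4 series has 157/18 = 8.7 lesions per patient, so a lesion-level interval that treats lesions as independent would also be wrong.

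**The case against.** The strongest reply is that the study is exploratory. Section 2.0 states its metabolic and diagnostic aims as exploration, the hypothesis sits in background text as one among possibly several, and the only aim in Section 2.0 that ranks the tracers concerns prediction of treatment response. Estimation without a decision rule is acceptable in such a study. This stands, and it is why no powered test is asked for. It does not excuse leaving out the estimate that the question calls for.

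A second reply is that the documents already lean towards same-patient, same-site comparison: Section 1.0 says so, and the pilot reported both tracers on the same lesions. Nowhere do they propose comparing CMET in a subset with FDG in everyone. This also stands. What is missing is the step from that intent to an analysis in Section 12.

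A reader might infer that the possible readings of the plan lead to opposite conclusions. The documents do not support that. If every patient has both scans, the difference of the two sensitivities equals the paired difference on the same units, so the direction cannot change. Under partial CMET use a reversal is arithmetically possible, but it needs a case-mix gap for which the documents give no figure. The simulation shows a spurious advantage against no difference, not a reversal.

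A reader might also take the 21-point pilot contrast as the likely bias. It should not be read so. The 71% is concordance over all bone lesions, while the 13 pilot lesions were new index lesions. The single CMET miss was later judged to be avascular necrosis. Leaving it out gives CMET 12/12 against FDG 11/12 or 10/12, that is 8 or 17 points.

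**Conclusion.** The concern holds in a limited form. Section 12 does not contain the comparison that Section 3.3 puts under study and Section 1.0 intends. Under partial CMET use, the planned estimates confound tracer with case mix. Under full dual scanning, they give the right difference without a valid interval.

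The size of the bias cannot be determined from the documents. A rate of 35-45% false findings for CMET rests on an assumed 14-point gap. It falls to 7-10% at 5 points and about 2% with none, and the figures are lower still if the two tracers agree closely within patients. They also assume all 265 patients contribute one unit each, whereas the hypothesis concerns the androgen-independent stratum, whose size is not stated. They should not be quoted as this trial's error rate. Because the remedy is cheap and uses planned data, the amendment is worth making.

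**What to change.** Reconcile Sections 1.0, 2.0, 3.3 and 12 on who receives CMET. Then add to Section 12:

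> The tracers are compared by the paired difference in sensitivity (CMET minus FDG) at baseline in androgen-independent patients who had both scans, over the same reference-positive lesions, at lesion level, with a 95% CI that accounts for clustering within patient. The patient-level paired difference is supportive. FDG sensitivity in FDG-only patients is reported descriptively and is not compared with CMET.

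The planned sensitivities for bone and for soft tissue stay as they are.

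The cost is a few sentences and one analysis; no scans are added. The drawback is that FDG-only patients do not contribute to the contrast, so its interval is wider. As an illustration with independent units and sensitivities near the pilot rates, 38 dually scanned patients give a 95% CI of −0.007 to 0.165 for a 3-0 discordant split and −0.074 to 0.232 for 6-3, half-widths of about 9 and 15 points. With 100 patients, the 7-0 and 15-8 splits above give about 5 and 9 points.
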